### **6.5 Discontinuation of Study Intervention**

If after appropriate consideration of study drug interruption/modification and consultation with the PTC Therapeutics medical monitor, it is not appropriate for a subject to continue with study treatment, then study drug should be permanently discontinued. After permanent discontinuation of study drug for a safety concern, and if the initial event was reported as a SAE, then a follow-up SAE report form should be completed. In the case of a treatment discontinuation due to an event that is not an SAE, the PTC Therapeutics medical monitor should be notified (see Section 7.3). In addition, details regarding the reasons for discontinuation and the adverse events (AEs) leading to the discontinuation should be recorded in the source documents and in the appropriate CRF. The Early Termination Visit CRF should be completed and appropriate follow-up, ie, at ~4 weeks as per protocol or until recovery from or stabilization of the AE, whichever comes last.

## 6.6 Participant Discontinuation/Withdrawal from the Study

All subjects who receive ataluren should remain in the study whenever possible. However:

- The parent/caregiver or legal guardian has the right to withdraw consent and discontinue ataluren at any time.
- If the subject's condition substantially worsens after initiating ataluren, the subject will be carefully evaluated by the Investigator. The subject will be withdrawn from treatment if continuing would place them at risk.
- The Investigator may withdraw the subject from ataluren, if, in the Investigator's clinical judgment, it is not in the subject's best interest to continue.
- Compliance will be evaluated at Visit 2, Visit 3, and at an early termination visit. Compliance is defined as a subject taking 80% to 120% of doses. In the event a subject becomes significantly noncompliant with ataluren administration, study procedures, or study requirements, the subject should be withdrawn from ataluren when the circumstances surrounding noncompliance increase risk to the subject or are anticipated to substantially compromise the interpretation of study results.
- If genotyping of the dystrophin gene indicates that patient does not carry a nonsense mutation in the gene.
- This study may be discontinued by the relevant regulatory authority, IRB/EC (Institutional Review Board/Ethics Committee), and/or PTC Therapeutics at any time.

The date ataluren is discontinued and the reason for discontinuation will be recorded in the source documents and in the electronic case report form (eCRF). The PTC medical monitor (or designee) should be informed via e-mail of when a subject discontinues study drug.

When ataluren is discontinued (regardless of the reason), the Investigator is expected to capture all the evaluations required at the end of study or follow-up and any additional evaluations should be completed that may be necessary to ensure that the subject is free of untoward effects. The subject should be encouraged to seek appropriate follow-up for any continuing health problems.

## 7 STUDY ASSESSMENT AND PROCEDURES

### 7.1 Schedule of Assessments and Study Parameters

**Table 1. Schedule of Assessments**

Study Procedure	Screening 	Visit 1 	Visit 2	Visit 3 End of Study 	Unscheduled Visit	Early Termination 	Follow-up 	Notes
Week (visit window)	-45 to -1 days	Baseline Week 1	Week 20 (± 14 days)	Week 40 (± 14 days)				
Eligibility								
Informed Consent	X							A signed and dated informed consent must be obtained before conducting any study procedures.
Inclusion/Exclusion	X							
Demographics	X							
Medical History	X							
Dystrophin genotyping	X							Documentation of the presence of a nonsense point mutation in the dystrophin gene as determined by gene sequencing must be reviewed and approved by sponsor prior to enrollment. Blood will be drawn for sequencing of the dystrophin gene to confirm the presence of a nonsense mutation.
Safety Assessments								
Physical Exam	X	X		X	X		X	Full physical-exam (including evaluation of cardiovascular system, chest and lungs, thyroid, abdomen, nervous system, skin and mucosae, musculoskeletal system, eyes, ears, nose, mouth, throat, spine, lymph nodes, extremities, and genitourinary) will be performed at screening. A Full physical-exam will be performed at screening and targeted physical exams at Visits 1 and Visit 3, and follow-up visit. A targeted exam will include nervous and musculoskeletal systems. At an unscheduled visit, physical exam will be done as necessary. Physical exam should be performed prior to rNSAA and TFTs assessments and biopsy.

**PTC124-GD-045-DMD  
Clinical Protocol**

Study Procedure	Screening	Visit 1	Visit 2	Visit 3 End of Study	Unscheduled Visit	Early Termination	Follow-up	Notes
Week (visit window)	-45 to -1 days	Baseline Week 1	Week 20 (± 14 days)	Week 40 (± 14 days)				
Clinical Labs	X	X		X	X	X		For Visit 1, Visit 3, and unscheduled and early termination visits, subjects should fast approximately 8 hours prior to assessment. Biochemistry and other laboratory assessments will be analyzed by the central laboratory. Biochemistry, hematology, and urinalysis laboratory assessments. Creatine kinase will be assessed via the UV method or an equivalent method. At an unscheduled visit, clinical laboratory assessments will be done as necessary. At Visit 1 and Visit 3, clinical laboratory assessments should be performed prior to biopsy.
Height/Weight/BMI		X	X	X		X		Height (in cm) and weight (in kg) will be measured at Visit 1, Visit 2, and Visit 3-Early Termination. If the subject is unable to stand, sitting arm span and ulna length should be assessed as surrogate measurements for height.
Vitals (HR & BP)		X		X	X			Vital signs will include systolic and diastolic blood pressure, pulse rate, and body temperature. The pulse rate and blood pressure determinations will be performed with the subject in a sitting position after a 5-minute rest. Blood pressure will be measured in triplicate and the average will be recorded. Vitals should be taken prior to rNSAA and TFTs assessments and biopsy.
AE/SAE Monitoring	X	X	X	X	X	X	X	AEs must be assessed and documented at each clinic visit. Subjects, parents/caregiver or legal guardian will be encouraged to report AEs of concern at any time in the intervals between visits.
Concomitant medications	X	X	X	X	X	X		Concomitant medications will need to be collected starting 30 days prior to first dose of study drug.
Efficacy Assessments								
Muscle biopsy		X		X				If a subject received ≥6 months of therapy but early terminated, a biopsy may be performed if subject, parents or legal guardian agrees.
rNSAA		X		X				
TFTs		X		X				

Study Procedure	Screening  Week (visit window)	Visit 1  Baseline Week 1	Visit 2 Week 20 (± 14 days)	Visit 3 End of Study  Week 40 (± 14 days)	Unscheduled Visit	Early Termination 	Follow-up 	Notes
Pharmacokinetic Assessments								
PK blood sampling		X		X				PK samples will be drawn on Visit 1, samples will be drawn pre-first study dose and 2 hours postdose, and on Visit 3 will be drawn pre-morning dose and 2 hours postdose.
Study Drug Administration								
Dispense Drug		X	X					First dose of study drug should be administered following completion of all Baseline (Visit 1) assessments. Because of potential changes in subject body weight over time, a dose adjustment may be made based on the subject's bodyweight at Visit 2 (Week 20). Central pharmacy to dispense drug direct to subject upon completion of Visit 2.
Unused Drug Return/ Compliance			X	X		X		All used and unused study drug kits and unused sachets will be returned as directed.

**Abbreviations:** AE, adverse event; BP, blood pressure; BMI, body mass index; HR, heart rate; PK, pharmacokinetic; rNSAA, Revised North Star Ambulatory Assessment; SAE, serious adverse event; TFT, timed-function tests; ██████████, ██████████ UV, urine volume

- 1 Screening procedures must take place within 45 days of baseline visit (Visit 1).
- 2 Any screening procedure completed within and including 7 days of Visit 1 can serve as baseline and does not need to be repeated at Visit 1.
- 3 Visit 1 and Visit 3 will be performed at ██████████. Subjects may have to return to the clinic for up to 3 days for completion of assessments and biopsy.
- 4 Early termination assessments should be performed for subjects who discontinue prematurely from the study.
- 5 The follow-up visit is for subjects who terminated early/discontinued from the study. Visit to occur ~30 days after termination/discontinuation or until recovery from or stabilization of the AE, whichever comes last. The follow-up visit will also occur for subjects who decided to discontinue ataluren therapy even if they completed assessments at Visit 3.

## 7.2 Safety Assessments and Other Assessments

Subjects will be monitored closely for AEs and laboratory abnormalities during the study.

For AEs and laboratory abnormalities, the investigator should use his/her judgment in determining whether the event or abnormality is clinically significant, whether diagnostic evaluation is warranted, and whether potential interruption of study drug therapy is appropriate. In general, life-threatening (Grade 4) or severe (Grade 3) AE or laboratory abnormalities should be considered clinically significant, although recurrent or persistent moderate events (Grade 2) may also be considered clinically significant in certain circumstances. Reference should be made to the Common Terminology Criteria for Adverse Events (CTCAE) Version 5.0 for grading the severity of adverse events and laboratory abnormalities. [CTCAE](#)

While specific monitoring, diagnostic testing, and supportive care measures must be instituted based on the clinical judgment of the investigator, investigators should contact the PTC Therapeutics medical monitor to obtain guidance and to ascertain whether similar events are being seen at other sites. The PTC Therapeutics medical monitor should be notified of any AE or laboratory abnormality that leads to dose interruption and should be apprised of ancillary laboratory or other diagnostic findings and the evolving data from any work-up of the initial abnormality. The PTC Therapeutics medical monitor may suggest review of the case with gastroenterology, endocrinology, nephrology consultants or with other experts (either at the site or retained by PTC Therapeutics).

Cases of decreased renal function have been observed in patients with nmCF receiving ataluren and IV aminoglycosides together with other antibiotics for cystic fibrosis exacerbations (Section 6.4.2). As a precaution, Table 2 provides information on actions to be taken in the event that abnormalities are noted in specified renal laboratory parameters. Thresholds are provided for interrupting study drug immediately or for interrupting study drug after confirmation of a value beyond the threshold. For AEs or laboratory abnormalities not listed in Table 2, the investigator should use his/her judgment in determining whether the event or abnormality is clinically significant, whether diagnostic evaluation is warranted, and whether potential interruption of study drug is appropriate.

**Table 2. Renal Monitoring Parameters and Actions To Be Taken**

Laboratory Parameter	Stop Study Drug Immediately, Confirm Abnormal Value, and Then Start Work-Up	Stop Study Drug After Confirming a Abnormal Value, and Then Start Work-Up
Serum cystatin C	>2.00 mg/L	>1.33 - 2.00 mg/L
Serum creatinine	≥ Grade 2 (≥1.5 x ULN for age)	Grade 1 (>ULN - 1.5 x ULN for age)
Serum BUN	≥3.0 x ULN	≥1.5 - 3.0 x ULN

**Abbreviations:** BUN = blood urea nitrogen; ULN = upper limit of normal

a Laboratory abnormalities may be confirmed immediately or at the next scheduled clinic visit based on investigator judgment.

## 7.3 Adverse Events and Serious Adverse Events

### 7.3.1 Definition of adverse events (AE)

An adverse event (AE) is any untoward medical occurrence associated with the use of a drug in humans, whether or not it is considered related to the drug. An AE can therefore be any unfavorable and unintended sign (including an abnormal laboratory finding), symptom, or disease in a study subject who is administered study drug in this study.

For this protocol, untoward medical occurrences that should be reported as AEs include the following:

- All AEs during the course of treatment with study drug administration
- All AEs resulting from medication misuse, abuse, withdrawal, or overdose, of study drug
- All AEs resulting from medication errors such as dispensing or administration error outside of what is described in the protocol
- Apparently unrelated illnesses, including worsening of a preexisting illness
- Injury or accidents. Note that if a medical condition is known to have caused the injury or accident (a fall secondary to dizziness), the medical condition (dizziness) and the accident (fall) should be reported as 2 separate AEs. The outcome of the accident (hip fracture secondary to the fall) should be recorded in source documents.
- Abnormalities in physiological testing or physical examination findings that require clinical intervention or further investigation (beyond ordering a repeat [confirmatory] test)
- Laboratory or electrocardiogram abnormalities that require clinical intervention or further investigation (beyond ordering a repeat [confirmatory] test) unless they are associated with an already reported clinical event. Laboratory abnormalities associated with a clinical event should be captured in the source documents. Laboratory abnormalities not requiring clinical intervention or further investigation will be captured as part of overall laboratory monitoring and should not be reported as AEs.
- A preexisting condition (eg, allergic rhinitis) must be noted on the appropriate CRF for Visit 1; however, it should not be reported as an AE unless the condition worsens or episodes increase in frequency during the AE reporting period. Diagnostic and therapeutic noninvasive and invasive procedures, such as surgery, should not be reported as AEs. However, the medical condition for which the procedure was performed should be reported if it meets the definition of an AE. For example, an acute appendicitis that occurs during the treatment with study

drug should be reported as the AE and the resulting appendectomy should be recorded in the source documents and eCRF. If a surgical procedure was planned prior to entry into the study, and the surgery is not performed because of a worsening of a baseline condition, this should not be reported as an AE. Note that, as described in Section 7.3.2 any hospitalization occurring as the consequence of an AE during the study period should be reported as an SAE.

Each AE is to be classified as serious or non-serious by the investigator using medical and scientific judgment.

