### 7.3.5 Recording Non-serious AEs and SAEs

All AEs (both serious and non-serious) that occur in subjects during the AE reporting period must be recorded, whether or not the event is considered drug related. In addition, any known untoward event that occurs subsequent to the AE reporting period that the investigator assesses as possibly related to the investigational drug/product should also be recorded as an AE.

All AEs are to be recorded in the source documents and on the eCRF using concise medical terminology; whenever possible, terms contained in the Medical Dictionary for Regulatory Activities (MedDRA) should be employed. In addition, the following information should be recorded:

- Indication of whether the event is serious or non-serious (see Section 7.3.2)
- Relationship to study drug (see Section 7.3.6)
- Severity of the event (see Section 7.3.7)
- Onset date
- Resolution date, or date of death
- Action taken
- Outcome of the event

Classification of the event as serious or non-serious determines the reporting procedures to be followed.

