### 7.3.7 Grading of severity of adverse event

The severity of AE will be graded using the CTCAE Version 5.0. For each episode, the highest severity grade attained should be reported.

If a CTCAE criterion does not exist, the investigator should use the grade or adjectives: Grade 1 (mild), Grade 2 (moderate), Grade 3 (severe), Grade 4 (life-threatening), or Grade 5 (fatal) to describe the maximum intensity of the AE. For purposes of consistency with the CTCAE, these intensity grades are defined in Table 4.

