### 8.1. Adverse Events

Adverse events will be coded using the MedDRA version 23.0. A treatment-emergent adverse event (TEAE) is defined as an adverse event that occurs or worsens on or after the first dose of study drug up to 6 weeks after the last dose of study drug. Any AE with an end date prior to the first dose of the study drug will not be considered as an TEAE.

The following summaries will be provided for TEAEs:

- TEAE overview
- TEAEs by SOC and PT

If a subject has multiple events under any given SOC and PT, the subject will be counted only once under that SOC and PT. If a subject has the same AE on multiple occasions, the highest severity reported on the CRFs (“life-threatening”, “severe”, “moderate”, “mild”, “unknown”, and “not reported”) will be presented in the summaries.

In addition, subjects with treatment-emergent SAE and TEAE leading to discontinuation will also be summarized.

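### Protocol 7.3.1 contradicts itself on whether an injury caused by an accident, such as a fracture after a fall, is an adverse event in its own right, so fracture counts depend on how each site reads it

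*Protocol*

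**What the plan says.** Protocol 7.3.1 opens with a broad definition of an AE and then lists what should be reported as one. One item begins "Injury or accidents". A note under that item covers the case where a medical condition is known to be the cause. There, "the medical condition (dizziness) and the accident (fall) should be reported as 2 separate AEs". The note ends: "The outcome of the accident (hip fracture secondary to the fall) should be recorded in source documents".

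Three other parts of the protocol bear on how to read that last sentence:

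- In the same list, laboratory findings that belong to an already reported clinical event are excepted from separate reporting: "Laboratory abnormalities associated with a clinical event should be captured in the source documents".
- In the appendicitis example at the end of 7.3.1, the appendicitis is the AE and "the resulting appendectomy should be recorded in the source documents and eCRF".
- Protocol 7.3.5 says "All AEs are to be recorded in the source documents and on the eCRF using concise medical terminology", and asks for seriousness, severity and outcome for each event.

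SAP 8.1 codes the AEs in MedDRA and plans an overview and "TEAEs by SOC and PT". It plans no separate summary of fractures or of injuries following accidents.

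**The concern.** A fracture is an untoward medical occurrence on any ordinary reading of the definition at the head of 7.3.1. The example nevertheless leaves it out of the count of AEs and gives it a destination, source documents, that does not feed the planned tables. A careful site that copies the example would enter dizziness and fall and stop there.

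Falls with injury are a foreseeable harm here. Subjects are boys aged 2 to under 8 years whose qualifying signs include proximal weakness and a waddling gait (Protocol 4.2). Corticosteroid use is anticipated in Protocol 6.4.1 and is a baseline variable and a subgroup in the SAP (6.4 and 7.1.2). If the rule is read differently across the roughly 10 sites, the fracture count partly reflects site interpretation. A fracture might also affect rNSAA loss-of-function counts or a timed test set to 30 seconds (SAP 7.3.1 and 7.3.2). An AE data set holding only a fall would explain such a result less well than one holding the fracture. Those endpoints are exploratory and descriptive.

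**Working it through.** The documents state no figure on this point, so there is none to reproduce. The check is to trace the protocol's own example through to the SAP tables under each available reading.

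**Reading A: the site follows the worked example.**
1. Two AEs are reported: the causing condition and the fall.
2. The fracture goes to source documents. The sentence does not mention the eCRF.
3. Under 7.3.5 the two reported AEs go on the eCRF, each with a term and a severity.
4. SAP 8.1 codes and tabulates those two terms. No fracture term exists to be counted.
5. Severity is graded under 7.3.7, where "For each episode, the highest severity grade attained should be reported". The fracture's grade can enter only if the site grades the fall by its consequence. Seriousness likewise can enter only through the fall record.

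**Reading B: the site follows the bullet's opening words or the procedures clause.**
1. The bullet names injury as well as accident among reportable items, and a fracture is an injury.
2. Elsewhere in 7.3.1, the condition that led to a procedure is reportable if it meets the AE definition. A fracture that is treated by a procedure meets that test.
3. The fracture is then an AE under 7.3.5, goes on the eCRF, and appears in the tables under its own term.

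**Which reading does the wording favour?** Two features of 7.3.1 support A for the example itself. The laboratory sentence uses source documents for findings that are not separate AEs, and the appendectomy sentence adds the eCRF when eCRF capture is wanted. The bullet's opening words and the general definition support B. The section therefore gives two answers for the same event.

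**Scale of one event.** Planned enrolment is approximately 15 to 20 (Protocol 8.2).
- 1/20 = 5.0%; 1/15 = 6.7%.
- One-sided 95% Clopper-Pearson upper bound with no events: 1 − 0.05^(1/n). For n = 20 this is 13.9%; for n = 15, 18.1%.
- With one event, the bound p solves (1 − p)^n + n·p·(1 − p)^(n − 1) = 0.05. For n = 20 this is 21.6%; for n = 15, 27.9%.

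If one child had a fracture that was not entered, the table would thus be compatible with a rate of up to 13.9% rather than 21.6% (n = 20), or 18.1% rather than 27.9% (n = 15). This illustrates a single hypothetical event. The SAP plans no such bounds.

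**The case against.** The strongest reply is that nothing in 7.3.1 forbids reporting the fracture. The sentence does not confine it to source documents. Where the section means to exclude something, as with procedures or minor laboratory findings, it says outright that these are not to be reported as AEs, and no such words attach to the fracture. The note is also conditional on a known medical cause, so a simple trip falls outside it. The appendectomy is an imperfect comparison, because it is a procedure, and in that example the diagnosis is the AE.

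All of this stands, and it limits the point. A reader might infer that the protocol keeps every fracture out of the AE tables. The documents do not support that: the bullet's opening words, the general definition and the procedures clause each give a route in, and a fracture without an accident is untouched by the note. A reader might also infer that a hospitalised fracture must carry the fall as its SAE term. Protocol 7.3.9 asks for the same term on both forms but does not say which term. Nor is understated severity certain, because the fall record could carry the grade.

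The SAP introduction also refers to the eCRF and its completion guidelines, which are not among the documents reviewed. An injury field may exist there.

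What the reply does not do is remove the conflict. The example counts two AEs, and the fracture is not one of them.

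**Conclusion.** The point holds as an internal contradiction with a practical consequence for the safety tables. Followed as written, the worked example yields no fracture term in the tables by SOC and PT. Followed by its opening words or by the procedures clause, the same section yields one. Which result appears depends on the site.

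The number of events affected is unknown because the documents give no fracture rate; each one would be 5.0% to 6.7% of the planned cohort. The conclusion assumes that the AE tables draw on eCRF records, and that the unseen completion guideline does not already settle the question. The effect is confined to safety reporting, and at most to the interpretation of exploratory function results. The primary analysis and the sample size are not touched. The change should be made, but the study's main conclusion does not rest on it.

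**What to change.** Replace the last sentence of the note in Protocol 7.3.1 with: *Any injury resulting from the accident (eg, hip fracture) should also be reported as a separate AE on the eCRF, with its own term, severity, seriousness and outcome, in addition to the accident and any causing medical condition.* This settles that the fall remains an AE and that the injury is added to it.

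Align the eCRF completion guideline with that sentence. Before database lock, query every recorded fall or accident for an associated injury; if enrolment is already complete, this step alone can recover missing terms.

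The cost is one sentence, a guideline edit, a few more AE records and queries, and possibly a slightly less favourable AE table. The change concerns recording only and alters no clinical management.
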